6.1.2.2 Continuous Variables

Continuous efficacy variables are:

- Raw value and change from baseline in the following assessments:
 - TJC (68 joints)
 - SJC (66 joints)
 - CRP
 - ESR
 - SGAP (VAS) (100 mm VAS)
 - SGA (VAS) (100 mm VAS)
 - PGA (VAS) (100 mm VAS)
 - HAQ-DI (See Section 10.5 Appendix 5: Computation of HAQ-DI Score)
 - DAS28-CRP score
 - DAS28-ESR score
 - SF-36v2®
 - SDAI score
 - CDAI score
 - WPAI score (See Section 10.7 Appendix 7: Computation of WPAI Scale Score)

6.1.2.3 Time to Event Variables

- Time to the first ACR20-CRP response up to Week 12
- Time to the first ACR50-CRP response up to Week 12
- Time to the first ACR70-CRP response up to Week 12
- Time to the first occurrence of DAS28-CRP < 2.6 up to Week 12
- Time to the first occurrence of SDAI score <= 3.3 up to Week 12
- Time to the first occurrence of CDAI score <= 2.8 up to Week 12
- Time to the first occurrence of ACR/EULAR score for remission up to Week 12

6.2 Safety Variables

- AEs
- Vital signs (body temperature, pulse rate and blood pressure in sitting position)
- Body weight
- 12-lead ECG
- Central ECG
- Chest radiography
- Laboratory assessments

Treatment emergent adverse events (TEAEs) will be defined as any adverse event that started or worsened in severity after initial dose of study drug or reference drug through Week52 or Withdrawal.

AE for the subjects who switched ASP015K 100 mg or ASP150 mg from Placebo at Week 12 will be handled as follows:

- AE onset before the first dose of week12 study drug will be considered to be occurred at Placebo.
- AE onset after the first dose of week12 study drug will be considered to be occurred at ASP015K 100 mg or 150 mg, which is switched treatment from Placebo.

A drug-related TEAE is defined as any TEAE with possible, probable or missing relationship to study drug or reference drug as assessed by the investigator.

Moreover, any TEAE with missing relationship to study drug or reference drug was counted as drug related (probable).

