5.4.3 Adverse Events

The survey period for AEs will be from the initiation of treatment with the study drug or reference drug to before the initiation of administration in the extension study or until the end of follow-up.

Events that occurred after treatment with the study drug or reference drug until before the initiation of administration in the extension study or until the end of follow-up will be recorded as AEs. Concurrent diseases that worsened during the study will also be recorded as AEs. AEs that occurred after the subject has completed the study plan or has been discharged from the hospital or the study center will not be recorded.

AEs that have not resolved before the initiation of administration in the extension study or at the end of follow-up must be followed-up until resolved or judged to be no longer clinically significant or until they become chronic to the extent that they can be fully characterized. If the event resolves during the study period, the date of resolution is to be entered in the eCRF.

See Appendix 4 “Liver Safety Monitoring and Assessment” for the assessment of AEs caused by DILI.

Herpes zoster should be entered as an AE information in the eCRF, and also, a separate Herpes Zoster (shingles) Worksheet should be prepared, and a copy should be submitted to the sponsor. If the sponsor considers necessary and requests for submission of forms for the purpose of providing additional information on other AEs, a form must be prepared to report to the sponsor.

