WHO-DD	World Health Organization Drug Dictionary
WPAI	Work Productivity and Activity Impairment Questionnaire

List of Key Terms

Terms	Definition of terms
Baseline	1) Values/findings observed prior to the initiation of study treatment, which are regarded as the starting point for comparison. 2) The time point at which those reference values/findings were observed.
Study period	The period of time from obtaining informed consent from the subject to the end of the final evaluation/observation specified in the protocol.
Investigational period	The period of time where major interests of protocol objectives are observed. In general, the subject will receive a test drug, comparative drug, or reference drug (possibly without randomization) during this period, which extends until the last post-treatment assessment is completed.
Follow-up period	The follow-up period will be 4 weeks (on a per-protocol basis) starting after the early-termination visit for withdrawn subjects and after the Week 52 visit for subjects who completed the study but are not willing to enroll into the extension study or those in the reference group who completed the study. For subjects who completed the study and wish to enroll into the extension study, the follow-up period will last for a maximum of 4 weeks starting after the Week 52 visit and ending at the initiation of the extension study treatment.
Subject	An individual who participates in a clinical study as a recipient of either the test drug(s) or reference drug(s), or as a control.
Week 12/ET	Week 12 or early termination before Week 12
EOT	Week 52 or early termination before Week 52
Study discontinuation	The act of concluding participation, prior to completion of all protocol-required elements, in a study by an enrolled subject. Four categories of discontinuation are distinguished: a) dropout: Active discontinuation by a subject (also a noun referring to such a discontinued subject); b) discontinuation initiated by the investigator or other responsible personnel (e.g., for cause); c) loss to follow-up: discontinuation of participation without notice or action by the subject; d) sponsor-initiated discontinuation. Note that subject discontinuation does not necessarily imply exclusion of subject data from analysis.
Variable	A characteristic under study that varies: any attribute, phenomenon, or event that can have different qualitative or quantitative values.

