7.5.1 Adverse Events

If an AE occurs on the same date as the initial dose date, the subject will be asked to select one of the following (see the eCRF page for AE): onset before initial dose of study drug or reference drug, onset after initial dose of study drug or reference drug. Any AEs occurring after initial dose of study drug or reference drug through the follow-up period will be considered treatment emergent.

Adverse events will be coded using the Medical Dictionary for Regulatory Activities (MedDRA).

All adverse events reported during the study period will be presented in subject listings.

Only TEAEs in the study period will be analyzed, and 2 types of analyses will be performed: TEAE occurrence analysis and TEAE per 100 patient-years analysis, as described below. TEAE occurrence analysis will be displayed by whole treatment period and by the following period. Primarily, TEAE occurrence analysis for Week 0 to Week 12 will be conducted in the view of comparison with placebo.

TEAE occurrence analysis for overall treatment period will be conducted in focus for ASP015K dose groups and reference group.

1. Week 0 to Week 12
2. Week 12 to Week 52 or Later

TEAE per 100 patient-years analysis will be displayed above category, and by overall period.

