7.5.1.2 Adverse Events Per 100 Patient-Years

In order to adjust for differences in subjects' durations in the study and the potential differential dropout rates between the treatment groups, TEAEs per 100 patient-years (PYs) will be calculated for each treatment group as follows:

Definition 1:

TEAEs per 100 PYs = $100 \times (\text{Number of subjects who had at least 1 incidence} / \text{Total PYs})$

Total PYs will be calculated by summing individual subjects' durations.

If subjects had at least 1 predefined AE, then the duration of these subjects are summed as from initial dose up to first incidence of predefined AEs.

If subjects had no predefined AE, then the duration of these subjects are summed as from initial dose through follow-up. Summed duration will be divided by 365.25 to represent per year.

Definition 2:

TEAEs per 100 PYs = $100 \times (\text{Number of TEAEs for all subjects in the treatment group} / \text{Total PYs in the treatment group})$.

For number of TEAEs for all subjects in the treatment group, multiple occurrences of the same TEAE in the same subject will be counted multiple times.

Total PYs will be calculated by summing subjects' durations in study through the follow-up period. Each subject's duration will be calculated as: $(\text{last date of follow-up in the study} - \text{date of initial dose of study drug} + 1) / 365.25$.

Patient-Year analysis will be calculated by Placebo, 100 mg, 150 mg, 100mg+150mg, ASP015K Total, Total.

The number of TEAEs and AEs per 100 PYs will be provided by Definition 2, for all TEAEs (if analyzable), by SOC and PT for each treatment group, ASP015K Total and Total.

Patient-Year analysis for following specified AE will also be conducted by Definition 1 with 95% confidence interval.

- Serious Infections
- Malignancies
- Herpes Zoster Related Disease (Herpes Zoster and Varicella)
- Herpes Zoster
- Varicella
- Infections That Require Intravenous Anti-infectious Therapy

Note: Definition will be provided in the Appendix 8.

Confidence Interval for TEAEs per 100 patient-years will be calculated for AE of special Interest based on following formula (assuming Poisson distribution).

- Upper limit of CI log (TEAEs per 100 PYs) : $exp\left(\log\left(\frac{A}{T}\right) + Z_{alpha} * \sqrt{\frac{1}{A}}\right)$
- Lower limit of CI log (TEAEs per 100 PYs) : $exp\left(\log\left(\frac{A}{T}\right) - Z_{alpha} * \sqrt{\frac{1}{A}}\right)$

A: Number of subjects who had at least 1 incidence

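### SAP 6.2 ends the TEAE window at Week 52 or withdrawal, but SAP 7.5.1 and the patient-year denominator run through follow-up; if 6.2 is applied, rates are diluted, more for etanercept than for ASP015K

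*SAP*

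**What the plan says.** **Two definitions of the event.** SAP 6.2 (Safety Variables) counts an adverse event as treatment emergent if it "started or worsened in severity after initial dose of study drug or reference drug through Week52 or Withdrawal". SAP 7.5.1 (Adverse Events) says: "Any AEs occurring after initial dose of study drug or reference drug through the follow-up period will be considered treatment emergent". Section 7.5.1 adds that only TEAEs are analysed, while all adverse events of the study period go into listings.

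**One denominator, reaching into follow-up.** SAP 7.5.1.2 gives two patient-year definitions.
- Definition 1 (events of special interest): "If subjects had no predefined AE, then the duration of these subjects are summed as from initial dose through follow-up". For a subject with an event: "If subjects had at least 1 predefined AE, then the duration of these subjects are summed as from initial dose up to first incidence".
- Definition 2 (all TEAEs): "Total PYs will be calculated by summing subjects' durations in study through the follow-up period".

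**Length of follow-up.** The SAP List of Key Terms states: "The follow-up period will be 4 weeks (on a per-protocol basis) starting after the early-termination visit for withdrawn subjects". The same four weeks apply to completers who do not enter the extension and to all reference-group completers. Completers who do enter it have at most four weeks, ending at the first extension dose. Footnote 2 of the Schedule of Assessments removes follow-up altogether when the extension starts immediately. Protocol 5.1.5 bars the reference group from the extension.

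**Collection.** Protocol 5.4.3 records adverse events from first dose to "before the initiation of administration in the extension study or until the end of follow-up".

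**The concern.** The two SAP sections give the same term different end dates, and the choice decides whether follow-up events enter the TEAE summaries. Under 6.2 the numerator stops at Week 52 or withdrawal while the denominator keeps adding days on which no event can count.

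The patient-year rates are there to adjust for unequal time in study and unequal dropout. A denominator that includes ineligible time works against that purpose, and the ineligible time is not spread evenly. By rule, every etanercept completer carries four weeks of it, whereas an ASP015K completer carries anything from none to four weeks. Table 22 (SAP Appendix 3) sets 100 mg, 150 mg and Reference side by side for the overall period.

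Counts are affected too. A serious infection or a fatal event that begins in the four weeks after withdrawal would be missing from the TEAE tables under 6.2.

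**Working it through.** The documents state no TEAE rate or patient-year total, so there is no planned figure to reproduce.

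**Which section is the outlier?**

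| Source | End point |
|---|---|
| SAP 6.2 | Week 52 or withdrawal |
| SAP 7.5.1, definition | End of follow-up |
| SAP 7.5.1, name of the second AE period | Extends beyond Week 52 |
| SAP 7.5.1.2, person-time | End of follow-up (Definition 1: first event, if there is one) |
| Protocol 5.4.3, collection | End of follow-up or first extension dose |

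Only 6.2 stops early.

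**Dilution for one subject if 6.2 is applied.** Let T be the days in the 6.2 window and F the follow-up days in the denominator. At a constant event rate, reported rate / true rate = T/(T + F). T is 365 for a completer (Week 52 is Day 365), and F is 28 for a full follow-up.
- Completer with full follow-up: 365/393 = 0.929, or 7.1% too low.
- Completer entering the extension at once: 365/365 = 1.000, no dilution.
- Subject withdrawn at Day 85: 85/113 = 0.752, or 24.8% too low. This applies equally in any arm.

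**Definition 1.** Event-free subjects add F and subjects with an event do not. With an exponential time to first event at an assumed 3 per 100 patient-years, T = 365 and F = 28:
- probability of an event by Day 365: 1 − exp(−0.03 × 365/365.25) = 0.0295;
- expected time at risk: 0.0295/(0.03/365.25) ≈ 359.6 days;
- added follow-up: (1 − 0.0295) × 28 ≈ 27.2 days;
- ratio: 359.6/(359.6 + 27.2) = 0.930.

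Stopping at the first event therefore hardly changes the result: 3.0 would be reported as about 2.8 per 100 patient-years.

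**Arm level, Definition 2.** Let d be the proportion withdrawn, w their mean withdrawal day, and r the proportion of completers entering the extension at once (r = 0 for etanercept). Then:
- mean window = (1 − d) × 365 + d × w;
- mean follow-up = d × 28 + (1 − d) × (1 − r) × 28.

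The documents give none of d, w or r. The table assumes the same d and w in both arms.

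| d, w | Etanercept too low by | ASP015K too low by, r = 0 / 0.5 / 0.9 / 1 | Inflation of ASP015K/etanercept ratio, same r |
|---|---|---|---|
| 0% | 7.1% | 7.1 / 3.7 / 0.8 / 0.0% | 1.000 / 1.037 / 1.069 / 1.077 |
| 20%, Day 169 | 7.9% | 7.9 / 4.9 / 2.3 / 1.7% | 1.000 / 1.033 / 1.060 / 1.068 |
| 30%, Day 85 | 9.1% | 9.1 / 6.1 / 3.6 / 2.9% | 1.000 / 1.033 / 1.061 / 1.068 |

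Worked cell (20%, Day 169, r = 0.9): the window is 0.8 × 365 + 0.2 × 169 = 325.8 days. ASP015K follow-up is 0.2 × 28 + 0.8 × 0.1 × 28 = 7.84 days, giving 325.8/333.64 = 0.977. Etanercept follow-up is 28 days, giving 325.8/353.8 = 0.921. The ratio is 0.977/0.921 = 1.06.

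**100 mg against 150 mg.** The rules are identical. With 10% against 20% withdrawals (mean Day 169, r = 0.9) the dilution would be 1.5% against 2.3%.

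**If events and person-time share an end date**, either one, the ratio is 1.000 in every arm.

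**The case against.** The best defence is that 6.2 may never be programmed. Section 7.5.1 is the AE analysis section, and the person-time rules and protocol collection agree with it. If analysts follow it, there is no dilution. That stands, and it makes the harm conditional. It does not settle which of two current definitions applies.

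Three stronger readings are tempting, and the documents do not support them.
- **Every arm is biased by its own amount.** The built-in difference is between etanercept and ASP015K only. The two ASP015K arms share one set of rules, and placebo is not a column in the overall patient-year analysis of Table 22.
- **Follow-up events are lost.** They are still collected under protocol 5.4.3 and listed under SAP 7.5.1. Under 6.2 they leave the summaries, not the record.
- **The main safety comparison is compromised.** SAP 7.5.1 makes Week 0 to Week 12 against placebo the primary AE view. There the choice of definition matters only for subjects who withdraw before Week 12. The etanercept comparison is descriptive, since SAP 7.1 makes statistical comparisons against placebo only.

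A fair objection to the remedy also stands in part. Running both windows through follow-up leaves off-drug time in the etanercept rate that immediate extension entrants do not have. If the off-drug event rate were half the on-drug rate (an assumption), a completer with follow-up would show (365 + 14)/393 = 0.964 of the on-drug rate, 3.6% low.

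**Conclusion.** The contradiction is real and unresolved, and 6.2 is the section out of line. Its numerical effect is modest and conditional. If 6.2 governs and the event rate is constant, a completer with full follow-up has a rate 7.1% too low, against 0% for an immediate extension entrant. Over 0 to 30% withdrawal and 0 to 100% extension entry, the ASP015K/etanercept rate ratio in the overall table is inflated by a factor of about 1.00 to 1.08. If 7.5.1 governs, the mismatch is zero.

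A reader might take the 7% as the expected error in the etanercept comparison. It is close to the top of the range, reached when nearly all ASP015K completers enter the extension at once. The definition should be corrected because it also decides which post-withdrawal events appear in the TEAE tables, but no confirmatory conclusion depends on it.

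**What to change.** 1. Amend SAP 6.2 to match 7.5.1 and protocol 5.4.3: a TEAE is an event with onset or worsening after the first dose through the end of follow-up, or until the first extension dose if that is earlier.
2. In SAP 7.5.1.2, state that events and person-time use the same end date in each analysis period. Table 22 plans a Week 0 to Week 12 patient-year analysis, but 7.5.1.2 gives its person-time no Week 12 end, so add that cut.
3. Add a supportive overall rate with both events and person-time cut at Week 52 or withdrawal. It shows whether the off-drug follow-up of etanercept completers matters.

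The cost is a few SAP sentences and one extra table, with no new data and no change to study conduct. The downside is that slightly more events are counted, and the main rate keeps etanercept follow-up time that immediate extension entrants do not contribute; item 3 addresses the latter.

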5.5 Adverse Events and Other Safety Aspects

5.5.1 Definition of Adverse Events (AEs)

An AE is defined as any untoward medical occurrence in a subject administered a study drug or reference drug that does not necessarily have a causal relationship with this treatment. An AE can therefore be any unfavorable and unintended sign (including an abnormal laboratory finding), symptom, or disease temporally associated with the use of a study drug or reference drug, whether or not related to the study drug or reference drug.

- CONFIDENTIAL -

An abnormality identified during a medical test (e.g., laboratory parameter, vital sign, ECG data, physical examination) should be defined as an AE only if the abnormality meets one of the following criteria:

- Induces clinical signs or symptoms
- Requires active intervention
- Requires suspension, interruption, or discontinuation of the study drug or reference drug
- The abnormality or laboratory test value is clinically significant based on the opinion of the investigator or other responsible personnel

The particulars to be noted with respect to the AE are the name of the event, date of onset, date of disappearance, severity (at peak time), seriousness, treatment of the study drug or reference drug, other treatment, outcome, causal relationship to the study drug or reference drug, and rationale for the assessment of causal relationship. The rationale for the assessment of the causal relationship does not need to be recorded for all AEs but only at the request of the sponsor. The severity of each event should be recorded on a scale of Grade 1 to Grade 5 in the eCRF, and the causal relationship to the study drug should be recorded as “Probable,” “Possible,” or “Not related” (see Section 5.5.3 Criteria for Causal Relationship to the Study Drug and Section 5.5.4 Criteria for Defining the Severity of an Adverse Event). The treatment of the AE (whether it was treated with pharmacotherapy or by other means) and the treatment of the study drug or reference drug should be recorded in the medical record or other source documents and in the eCRF. The outcome should be recorded in the medical record or other source documents and in the eCRF as “resolved,” “alleviated,” “unresolved,” “resolved but with late effects,” “death,” or “unknown.”

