5.5.6 Follow-up of Adverse Events

All AEs occurring during or after the subject has discontinued the study are to be followed up until resolved or judged to be no longer clinically significant, or until they become chronic to the extent that they can be fully characterized.

If during AE follow-up, the adverse event progresses to an "SAE", or if a subject experiences a new SAE, the investigator must immediately report the information to the Sponsor/delegated CRO.

Even if the subject does not return to normal or to his/her previous state, follow-up can be considered no longer necessary or finished when the following procedures have been taken:

[1] Follow-up is considered no longer necessary if:

The investigator/sub-investigator judges that follow-up of the subject is no longer necessary because the AE's relationship to the study drug or reference drug could be ruled out, and this judgment is considered appropriate by the sponsor.

[2] Follow-up is considered finished if:

The investigator judges that follow-up of the subject is no longer necessary based on the progression made during follow-up; the reason for such a judgment is entered as a comment in the CRF for follow-up, and the sponsor judges that the reason is acceptable with regard to the safety of the subject concerned.

For details of follow-up of DILI (medical history, concomitant medications, history of alcohol intake and narcotic use), see Appendix 4 "Liver Safety Monitoring and Assessment."

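### Placebo switchers' adverse events are assigned by onset alone but graded at their peak, so worsening on ASP015K is reported as a placebo event

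*SAP*

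**What the plan says.** SAP 6.2 gives two rules for subjects who move from placebo to ASP015K at Week 12. The first is "AE onset before the first dose of week12 study drug will be considered to be occurred at Placebo". The second is "AE onset after the first dose of week12 study drug will be considered to be occurred at ASP015K 100 mg or 150 mg". Both turn on onset.

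The same section defines a treatment-emergent event as "any adverse event that started or worsened in severity after initial dose of study drug or reference drug through Week52 or Withdrawal". Worsening counts, but it is measured from the initial dose, which for these subjects is placebo.

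Protocol 5.5.1 lists what is noted for each event, including "date of disappearance, severity (at peak time), seriousness, treatment of the study drug or reference drug". It adds: "The severity of each event should be recorded on a scale of Grade 1 to Grade 5 in the eCRF". Protocol 5.5.6 recognises that an existing event can change status ("If during AE follow-up, the adverse event progresses to an" SAE) and treats this as distinct from a new SAE.

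SAP 7.5.1 makes Week 0 to 12 the main safety comparison with placebo. In Tables 20 and 21 (SAP Appendix 3) that period has a Placebo column. Week 12 onward has two placebo-to-ASP015K columns for the rows it covers, and nearly all Overall entries leave the switchers out.

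**The concern.** The definition of a treatment-emergent event admits worsening, but the rule that places a switcher's event on placebo or ASP015K ignores it. Because severity is a single peak value, a grade reached on ASP015K is carried back to the treatment taken at onset. Seriousness, a single item per event, follows the same path.

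All placebo subjects who reach Week 12 switch, so Week 0 to 12 is the trial's only placebo-controlled safety period. What is at stake is the placebo count of severe and serious events in that period, and the completeness of the switchers' columns afterwards. The problem arises even when every date is complete.

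**Working it through.** The plan states no figure on this point, so the check has three parts: follow one event through the rules, size the group affected, and look at the effect on the comparison.

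**1. One event (illustrative days).** Onset on Day 80 on placebo, Grade 1; switch on Day 85; Grade 3 and hospitalised on Day 100 on ASP015K.

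- Record: onset Day 80, severity Grade 3 (peak), serious.
- Week 0 to 12: counted under Placebo, as Grade 3 or higher and as serious (SAP Table 20).
- Week 12 onward: not in a placebo-to-ASP015K column, because onset preceded the switch.
- Overall tables for 100 mg, 150 mg and reference: switchers are not shown.
- If it is an infection: the serious-infections row of SAP Table 21 has no Week 12 to 52 entry, so in that row it can appear only under Placebo.

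**2. How many subjects.** Inputs from the Phase IIb study (Protocol 1.3): 64.3% of placebo subjects had an AE, and 10 (17.9%) discontinued for AEs. Planned placebo group: 100 (SAP 3.2). Assumed, because the documents give neither: 20 to 40% of subjects with an AE have one ongoing at the switch, and 5 to 10% of those worsen in any degree.

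- Switchers = 100 × (1 − 0.179) ≈ 82, allowing only for AE discontinuations.
- Any worsening, low: 82 × 0.643 × 0.20 × 0.05 = 0.5.
- Any worsening, high: 82 × 0.643 × 0.40 × 0.10 = 2.1.

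For serious worsening, a rough proxy is the Phase IIb share of subjects with an AE who had an SAE. The group sizes implied by its counts and percentages are 56, 55, 57, 55 and 58 (sum 281). Subjects with any AE are then 36 + 39 + 37 + 29 + 39 = 180, and subjects with an SAE are 1 + 1 + 2 + 3 + 0 = 7. The share is 7/180 = 3.9%, about 4%.

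- Low: 82 × 0.643 × 0.20 × 0.04 = 0.4.
- High: 82 × 0.643 × 0.40 × 0.04 = 0.8.

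This proxy is probably generous, since it includes events that were serious from the start.

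**3. What one case does.** The Phase IIb placebo SAE rate is 1/56 = 1.79%, or about 2 per 100. One reassigned subject with no other SAE gives 1.79 + 1.00 = 2.79 per 100, and 2.79/1.79 = 1.56.

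For the comparison, let *a* and *p* be the subjects per 100 whose later grade or seriousness is pulled into the Week 0 to 12 ASP015K and Placebo columns. The difference (ASP015K minus placebo) changes by *a* − *p*. As an illustration, take the Phase IIb 100 mg rate of 3/55 = 5.45% against 1.79%:

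| Case | 100 mg | Placebo | Difference | Ratio |
|---|---|---|---|---|
| No carry-back | 5.45 | 1.79 | 3.67 | 3.05 |
| *a* = *p* = 1 | 6.45 | 2.79 | 3.67 | 2.32 |
| *a* = 0, *p* = 1 | 5.45 | 2.79 | 2.67 | 1.96 |

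Equal carry-back leaves the difference unchanged and dilutes the ratio. Carry-back to placebo alone shrinks both.

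**The case against.** The strongest reply is that peak grading applies to every arm. SAP 7.5.1 has no separate rule for subjects who do not switch, and on the natural reading an event starting on Day 80 in the 100 mg or 150 mg arm and peaking on Day 100 also enters Week 0 to 12 at its later grade. A reader might infer that the rule flatters the drug in both period tables. The documents do not support that for Week 0 to 12: *a* − *p* is unknown in sign. It remains true that the ASP015K-arm event sits under the drug being taken when it peaked, and the switcher's event does not.

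Other replies have partial force:

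- The CRF instructions (Protocol 8.1.5) are not among the documents and could require a worsened event to be entered afresh. Neither the protocol nor the SAP says so.
- The peak-time qualifier is attached to severity only. For seriousness the point rests on the single item together with Protocol 5.5.6.
- Worsened concurrent diseases are recorded as AEs (Protocol 5.4.3), but these are conditions uncured at the start of treatment (Protocol 5.2.2). An event that began on placebo is not covered.
- Laboratory minima and maxima up to Week 12 stop at the first Week 12 dose (SAP 7.11.6), which protects laboratory signals but not AE tables.
- Withdrawals are also tabulated by treatment sequence (SAP 7.2.1), and all AEs are listed (SAP 7.5.1). Neither corrects the severity or seriousness summaries.

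**Conclusion.** The point holds in limited form. As written, the rules give a wrong attribution for switchers' events that worsen after the switch, and the error moves such events onto placebo and off ASP015K. The under-count in the placebo-to-ASP015K columns follows directly. The effect on the Week 0 to 12 difference cannot be signed from the documents.

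The size is probably small: about 0.5 to 2 subjects with any worsening, fewer becoming serious. The range rests on assumed shares for ongoing and worsening events, on Phase IIb rates, and on 82 switchers. It should not be read as a forecast of serious cases. The reason to act is that, with about 2 serious placebo cases expected per 100, one misplaced case raises that count by about half.

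**What to change.** In SAP 6.2, add that an increase in grade or seriousness after the first Week 12 dose counts as a treatment-emergent event under the switched treatment. Keep the pre-switch grade and seriousness for placebo. Have the CRF instructions require such worsening to be entered as a new record with its own date.

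The planned study period ended in December 2017 and the current SAP is dated January 2018, so records may no longer be open to change. In that case, list the events ongoing at the switch and add a sensitivity table that attributes them by the date of worsening or of becoming serious, where known.

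The cost is slightly more AE records, higher event counts under Definition 2 of the patient-year analysis (SAP 7.5.1.2), and some subjects counted under both treatments. A footnote should state this. Retrospective queries for dates of grade change would cost more than the listing and sensitivity table.
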